### **9.5.2 Efficacy**

Efficacy variables will be presented for both the FAS and PPS analyses sets and include:

- DAS28-CRP, DAS28-ESR
- ACR20, ACR50, ACR70 (CRP & ESR) response rate
- CRP, ESR
- HAQ-DI
- FACIT Fatigue scale.

Incidence rates over time shall be presented for ACR 20/50/70 and DAS28-CRP EULAR defined criteria. Summary statistics of absolute and change from baseline for DAS28-CRP & ESR and CRP & ESR values will be provided.

For Treatment period 2 summary statistics of DAS28-CRP & ESR scores changes from Week 24 at Week 48 will be presented, in addition to incidence rates for ACR 20/50/70 at Week 48.

The quality of life assessments HAQ-DI and FACIT Fatigue Scale will be summarized for absolute values and change from baseline at Week 4, 12 and 24 and for change from Week 24 at Week 48. In addition incidence rates of patients achieving a HAQ-DI score of  $\leq 0.5$  and a score improvement of  $> 0.3$  shall be presented.

### **9.5.3 Safety**

All safety evaluations will be performed on the SAF analysis sets.

#### **Adverse events**

Treatment Emergent AEs (TEAE) defined as events started after the first dose of study treatment or events present prior to the first dose of study treatment but increased in severity, will be summarized. However all AEs recorded will be listed.

AEs will be summarized by primary system organ class and preferred term for:

- TEAEs
- TEAEs by maximum severity
- Treatment-related TEAEs
- SAEs
- TEAEs leading to dose adjustment/interruption
- TEAEs leading to premature discontinuation
- deaths

If a patient reported more than one adverse event within the same primary system organ class/preferred term, the patient will be counted only once with the greatest severity at the system organ class level/preferred term, where applicable.

## **Injection Site Reactions**

ISRs will be summarized by presenting the number and percentage of patients experiencing any ISR and by category. Summaries will also be presented by severity and for treatment-related ISRs.

## **Laboratory data**

Summary statistics for absolute and change from baseline by visit will be presented. In addition qualitative laboratory results will be summarized by visit. The incidence of patients with abnormal clinically notable laboratory values will be summarized.

## **Vital signs**

Summary statistics of change from baseline for vital sign measurements by visit will be presented. Abnormal vital sign measurements shall be summarized.

## **Electrocardiogram**

[figure not shown]
ECG will be summarized for ECG variables by visit and treatment group.

### **9.5.4 Immunogenicity**

Full ADA formation data and the titer and neutralization potential (as assessed by a neutralizing antibody (NAb) assay) of all confirmed positive binding results will be reported in the study CSR.

### **9.5.5 Pharmacokinetics**

[figure not shown]
No formal PK will be performed. Figures will be generated to illustrate the time course of adalimumab trough levels. The trough serum levels at selected visits will be evaluated using descriptive statistics.

## **9.6 Sample size calculation**

The sample size for this study is based on an expected difference of zero and common SD of 1.30 for the DAS28-CRP change from baseline at Week 12 (ReAct study), an equivalence margin of 0.6 and assumed loss of 20% patients from the per-protocol analysis set. A 0.6 change in DAS28-CRP score is considered as the minimum clinically meaningful difference by EULAR criteria and is therefore used as the equivalence margin limits [0.6,-0.6].

In order to fulfil FDA regulatory requirements for establishing therapeutic equivalence (e.g. using 90% confidence interval), a sample size of 154 patients per treatment group (to maintain

[figure not shown]
overall 246 evaluable patients for the primary endpoint analysis) will have 95% power to test the equivalence between GP2017 and US-licensed Humira®.

In order to fulfil EMA regulatory requirements for establishing therapeutic equivalence (e.g. using 95% confidence interval), a sample size of 154 patients per treatment group (to maintain overall 246 evaluable patients for the primary endpoint analysis) will have 90% power to test the equivalence between GP2017 and US-licensed Humira®.

## 9.7 Power for analysis of critical secondary variables

From Burmester et al (2014) the standard deviation at 6 months, i.e. roughly Week 24, was calculated as 1.5. This compares with the value of 1.3 found for the Week 12 assessment (see Section 9.6). However, it is difficult to estimate the common SD for the AUEC because this will depend on the correlation between the DAS28 values for the same subject at different visits. Assuming the correlation lies between 0 and 1, then common SD values between around 0.7 to 1.4 seem likely. Figure 9-1 below shows the resulting power for different values of the common SD with 246 evaluable patients when calculating both a 90% and 95% confidence interval. It is clear that there is always sufficient power (80%) to demonstrate equivalence using the 90% confidence interval, and that the power will also most likely be sufficient using the 95% confidence interval.

**Figure 9-1 Power of AUEC analysis for various common standard deviations**

## 9.8 Interim analysis

No interim analysis is planned.

## **10 Ethical considerations**

### **10.1 Regulatory and ethical compliance**

This clinical study was designed and shall be implemented and reported in accordance with the ICH Harmonized Tripartite Guidelines for Good Clinical Practice, with applicable local regulations (including European Directive 2001/20/EC, US Code of Federal Regulations Title 21, and Japanese Ministry of Health, Labor, and Welfare), and with the ethical principles laid down in the Declaration of Helsinki.

### **10.2 Informed consent procedures**

Eligible patients may only be included in the study after providing written (witnessed, where required by law or regulation), IRB/IEC/REB-approved informed consent, or, if incapable of doing so, after such consent has been provided by a legally acceptable representative of the patient. In cases where the patient's representative gives consent, the patient should be informed about the study to the extent possible given his/her understanding. If the patient is capable of doing so, he/she should indicate assent by personally signing and dating the written informed consent document or a separate assent form. Informed consent must be obtained before conducting any study-specific procedures (i.e. any of the procedures described in the protocol). The process of obtaining informed consent should be documented in the patient source documents.

The sponsor will provide to investigators in a separate document a proposed informed consent form that complies with the ICH GCP guideline and regulatory requirements and is considered appropriate for this study. Any changes to the proposed consent form suggested by the investigator must be agreed to by the sponsor before submission to the IRB/IEC/REB, and a copy of the approved version must be provided to the sponsor (or CRO working on behalf of the sponsor) after IRB/IEC/REB approval.

Women of child bearing potential should be informed that taking the study drug may involve unknown risks to the fetus if pregnancy were to occur during the study and agree that in order to participate in the study they must adhere to the contraception requirement for the duration of the study and up to 70 days after the end of study. If there is any question that the patient will not reliably comply, they should not be entered in the study.

The "Information for female partners of male study participants" document should be given to male participants as part of the informed consent process with the request that they share it with their female partners. In case a partner of a male study participant becomes pregnant during the study, consent of the pregnant partner should be sought to collect information about the pregnancy, the birth and health of the baby.

### **10.3 Responsibilities of the investigator and IRB/IEC/REB**

The protocol and the proposed informed consent form must be reviewed and approved by a properly constituted IRB/IEC/REB before study start. A signed and dated statement that the protocol and informed consent have been approved by the IRB/IEC/REB must be given to the sponsor or delegated CRO before study initiation. Prior to study start, the investigator is

required to sign a protocol signature page confirming his/her agreement to conduct the study in accordance with these documents and all of the instructions and procedures found in this protocol and to give access to all relevant data and records to monitors, auditors, other designated agents of the sponsor or CRO, IRBs/IECs/REBs, and regulatory authorities as required. If an inspection of the clinical site is requested by a regulatory authority, the investigator must inform the sponsor or designated CRO immediately that this request has been made.

#### **10.4 Publication of study protocol and results**

The sponsor assures that the key design elements of this protocol will be posted in a publicly accessible database such as clinicaltrials.gov. Study results containing primary outcome measure will be published on clinicaltrials.gov within 12 months of primary completion date (defined as the date when all study patients have completed Week 12/ EoS (Visit 16) whichever is earlier). After finalization of the study report, the results of this trial will be submitted for publication and posted in a publicly accessible database of clinical trial results.

### **11 Protocol adherence**

Investigators will apply due diligence to avoid protocol deviations. Under no circumstances should the investigator contact the sponsor or its representatives monitoring the trial to request approval of a protocol deviation, as requests to approve deviations will not be granted, except when necessary to eliminate immediate hazards to the subjects.

This protocol defines the study objectives, the study procedures and the data to be collected on study participants. Under no circumstances should an investigator collect additional data or conduct any additional procedures for any research related purpose involving any investigational drugs.

If the investigator feels a protocol deviation would improve the conduct of the study this must be considered a protocol amendment, and unless such an amendment is agreed upon by the sponsor and approved by the Heath Authority where required, and the IRB/IEC/REB it cannot be implemented. All significant protocol deviations will be recorded and reported in the Clinical Study Report.

#### **11.1 Protocol Amendments**

Any change or addition to the protocol can only be made in a written protocol amendment that must be approved by the sponsor, Health Authorities where required, and the IRB/IEC/REB. Only amendments that are required for patient safety may be implemented prior to Health Authority and IRB/IEC/REB approval. Notwithstanding the need for approval of formal protocol amendments, the investigator is expected to take any immediate action required for the safety of any patient included in this study, even if this action represents a deviation from the protocol. In such cases, the sponsor should be notified of this action and the applicable IRB/IEC/REB should be informed as required per local regulations.

## Appendix 1: Clinically notable laboratory values

The following criteria will be used to define expanded limits and notable abnormalities of key laboratory tests.

Clinically notable values will be forwarded to the Sponsor at the same time that they are sent to investigators by Central Laboratory.

Clinically notable laboratory values should be documented as AE if the laboratory change has been confirmed by 3 repeated measurements at subsequent per-protocol visits. In subjects who already had abnormal laboratory parameters (eg CTC AE grade 1) at screening, laboratory change to CTC AE grade 2, confirmed by 3 repeated measurements should be considered clinical relevant and documented as AE. At the discretion of investigator, a laboratory change can be considered an AE already prior to confirmation by 3 repeated measurements.

**Table 12-1 Notable laboratory values for subjects with value within limits of normal at baseline**

Laboratory variable	Standard units	SI units
Aspartate aminotransferase	> 3 x ULN	> 3 x ULN
Alanine aminotransferase	> 3 x ULN	> 3 x ULN
Total Bilirubin	> 1.5 x ULN	> 1.5 x ULN
Alkaline Phosphatase	> 2.5 x ULN	> 2.5 x ULN
Creatinine (serum)	> 50% above baseline	> 50% above baseline
Potassium	< 3.0 mEq/L > 6.0 mEq/L	< 3.0 mmol/L > 6.0 mmol/L
Sodium	< 130 mEq/L > 150 mEq/L	< 130 mmol/L > 150 mmol/L
Calcium	<8 mg/dL >11.5 mg/dL	<2 mmol/L >2.9 mmol/L
Hemoglobin	> 20 g/L decrease from baseline	> 20 g/L decrease from baseline
Red Blood Cell count	> 20% below baseline	> 20% below baseline
Platelet count	< LLN	< LLN
White Blood Cell count	< 0.8 x LLN	< 0.8 x LLN
Absolute Neutrophil count	< 0.9 x LLN	< 0.9 x LLN
Absolute Lymphocyte count	> 1.1 x ULN	> 1.1 x ULN
Total Cholesterol	≥ 350 mg/dL	≥ 9.1 mmol/L

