### 4.1 Inclusion criteria

Patients eligible for inclusion in this study have to fulfill all of the following criteria:

1. Patients at least 18 years of age at screening who have given written informed consent (ICF) before any study related procedure is performed
2. Patients must have been diagnosed with RA according to the ACR 1987 or ACR/EULAR 2010 modified criteria  $\geq 6$  months prior to screening
3. Patients must have active disease, defined as DAS28-CRP  $\geq 3.2$  at the time of screening
4. Patients must have CRP levels above 5mg/l or ESR levels above the upper limits of normal as determined by a central lab for CRP and locally for ESR at screening
5. Patients must have had inadequate clinical response to MTX 10 - 25 mg/week after appropriate dose escalation according to local standards. Patients are required to have been on MTX therapy for  $\geq 3$  months and on a stable dose for at least 4 weeks prior to and at baseline. Patients, who failed any other DMARD treatment used alone or in combination with MTX, will be allowed to enter into the study after an appropriate wash-out period as defined in [Table 5-2](#) prior to baseline
6. Patients must be on a stable dose of folic acid ( $\geq 5$  mg per week) prior to baseline and must continue on a stable dose during the course of the study
7. Patients taking regular NSAIDs, COX-2 inhibitors, paracetamol/acetaminophen for treatment of RA symptoms are required to be on stable dose for at least 4 weeks before baseline
8. Patients who are willing to remain compliant throughout the study and after study completion with the safety precautions outlined in the local MTX label, particularly in relation to contraception requirements to prevent fathering a child or becoming pregnant. See Section [10.2](#) for details.
9. Patients must have following parameters at screening visit:

- Hemoglobin  $\geq$  10g/dl
- White blood count (WBC)  $\geq$  3,500/ $\mu$ l, neutrophil count  $\geq$  1,500/ $\mu$ l
- AST, ALT  $\leq$  2.5 x ULN
- Serum creatinine level  $\leq$  176.8  $\mu$ mol/L (2.0 mg/dL)
- Negative QuantiFERON®-TB Gold test (QFT)
- Negative imaging (e.g. chest X-ray, chest Computerized Tomography(CT) scan, Magnetic Resonance Imaging (MRI)) for tuberculosis

NOTE: in case imaging was done before screening, it must not be older than 3 months prior to randomization (baseline).

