2.1.2 General considerations

Raw data listings, summary tables, figures and statistical tests will be generated using the SAS® Version 9.4 or higher.

All clinical data, including laboratory, immunogenicity, and pharmacokinetics data will be provided as raw data from an external database. CDISC SDTM 3.1.2 amendment 1 compliant SAS® datasets will be prepared. The final SDTM files will also include variables indicating the actual and planned treatment assigned.

Coding of corresponding data (e.g. by Medical Dictionary for Regulatory Activities [MedDRA] or World Health Organization [WHO]-drug dictionary), and ATC coding is included in the SDTM datasets.

Appropriate SAS® programs will be prepared and validated according to standard operating procedures.

The following descriptive statistics will be shown in summary tables:

- Continuous variables: n (number of patients with evaluable data), mean, standard deviation (SD), minimum, median, maximum. Quartiles will be presented as appropriate.
- Categorical variables: Count and percentage of each category. A row denoted “Missing” will be included in count tabulations where necessary to account for dropouts and missing values. Unless otherwise specified, the denominator for all percentages will be the number of patients in the treatment group within the analysis set of interest. Percentages will not be provided if the number is zero.

The same number of decimal places as in the raw data will be presented when reporting minimum and maximum, 1 more decimal place than in the raw data will be presented when reporting mean, median and quartiles, and 2 more decimal places than in the raw data will be presented when reporting SD and SE.

For the derived variables, appropriate precision should be provided in CSR appendix data listing. E.g., for the DAS28-CRP and DAS28-ESR, 2 decimal places will be kept in the data listing, the decimal places of the descriptive statistics will then follow the rules above accordingly (i.e., treat raw data as 2 decimal places).

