4.6.2.2 Laboratory data

Results from the central laboratory will be included in the reporting of this study. The summaries presenting a number of patients with new notable abnormalities (according to the protocol), as well as shift tables by toxicity grades will be presented for hematology and serum chemistry by treatment group for each Study Period. Standard units will be used for presentation. Box plots of parameters of interest will be done by treatment and study period. The laboratory results below the LLOQ will be imputed as zero, the laboratory results above the upper detection limit will be imputed as upper detection limit.

All laboratory data (including urinalysis) will be listed. Notable abnormalities will be listed in addition.

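### Read literally, the notable-laboratory-value summary leaves out patients abnormal at baseline but keeps them in the percentage denominator, so the incidence is understated in both arms

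*Protocol*

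**What the plan says.** - **Population of the limits.** Table 12-1 is the only table of notable limits in the protocol. Its title is "Notable laboratory values for subjects with value within limits of normal at baseline". There is no parallel table for patients outside normal limits at baseline.
- **Type of limit.** Some limits are fixed against the laboratory range; for AST and ALT the limit is > 3 x ULN. Others are relative to the patient's own baseline (hemoglobin, red cell count, creatinine).
- **Entry.** Inclusion criterion 9 (Protocol 4.1) sets these screening limits: "AST, ALT $\leq$ 2.5 x ULN", "Hemoglobin $\geq$ 10g/dl", "neutrophil count $\geq$ 1,500/ $\mu$ l", and WBC of at least 3,500/µl. Patients abnormal on these tests can therefore be randomized.
- **What is counted.** For the blood-count and chemistry panels, split by arm and period, the planning sentence in SAP 4.6.2.2 opens: "The summaries presenting a number of patients with new notable abnormalities (according to the protocol), as well as shift tables by toxicity grades will be".
- **Denominator.** SAP 2.1.2, unless something else is specified: "the denominator for all percentages will be the number of patients in the treatment group within the analysis set of interest". SAP 4.6.2.2 specifies nothing else.
- **Protocol commitment.** Protocol 9.5.3 plans the incidence of patients with notable values, without restricting it by baseline status, and change from baseline by visit.
- **Second source.** SAP 2.3.2.2 sends the reader to the laboratory manual to identify notable values, while SAP 4.6.2.2 points to the protocol. The manual is not among the documents.

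**The concern.** The numerator and the denominator refer to different patients. A patient whose ALT is 2.0 x ULN at baseline and later exceeds 3 x ULN has crossed the numeric limit, but the title of Table 12-1 does not cover that patient. A programmer who follows the title will not count the event, and the patient still contributes to the denominator of any percentage. The same holds for a patient with low hemoglobin at baseline who then falls by more than 20 g/L.

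Comparing laboratory parameters between the two products is a stated secondary objective (Protocol 2.2). If events in patients abnormal at baseline are absent from the table, so is any difference between the arms among those patients. All patients are also on background MTX.

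**Working it through.** The documents give no laboratory incidence, no expected count and no share of patients abnormal at baseline, so there is no planned figure to reproduce. The check is a reading of the rules plus simple arithmetic.

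**1. The literal count.** For a given test, let f be the share of patients abnormal at baseline, rN the rate of crossing the limit among those normal at baseline, and rA the rate among those abnormal at baseline.
- Table as literally written: (1 − f) x rN
- All patients counted: (1 − f) x rN + f x rA
- Left out per arm: 154 x f x rA (154 is the planned number per arm)

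**2. Illustration.** The values of f, rN and rA are assumptions and do not come from the documents. rN is 3% throughout.

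| f | rA | Literal | All counted | Left out per arm | Share of events left out |
|---|---|---|---|---|---|
| 5% | 3% | 2.85% | 3.0% | 0.2 | 5% |
| 10% | 10% | 2.7% | 3.7% | 1.5 | 27% |
| 20% | 10% | 2.4% | 4.4% | 3.1 | 45% |
| 30% | 20% | 2.1% | 8.1% | 9.2 | 74% |

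Last row: 0.70 x 3% = 2.1%; 0.30 x 20% = 6.0%; sum 8.1%; 154 x 0.30 x 0.20 = 9.2; 6.0/8.1 = 74%. Restricting the denominator to patients normal at baseline would give 3.0% in every row. The mismatch therefore lowers the reported rate even for the patients the table does cover.

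**3. Who is left out.**
- *AST and ALT.* The rise needed to reach 3 x ULN from baseline b (in multiples of ULN) is 3/b − 1: 200% from 1.0, 100% from 1.5, 50% from 2.0 and 20% from 2.5. The patients outside the title are those nearest the limit.
- *WBC and neutrophils.* The notable limits are 0.8 x LLN and 0.9 x LLN. The entry floor already lies below the notable limit only if the LLN exceeds 3,500/0.8 = 4,375/µl, or 1,500/0.9 = about 1,667/µl. The LLNs are not given, so nearness to the limit is not shown.
- *Hemoglobin, red cells, creatinine.* These limits are changes from the patient's own baseline. A patient abnormal at baseline is no nearer to them.

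**4. What the other outputs recover.**
- Shift tables by toxicity grade carry no baseline restriction. They show movement between grades, not the notable-value incidence, and the SAP does not name the grading system.
- Change-from-baseline summaries are in Protocol 9.5.3 but are not listed in SAP 4.6.2.2, which adds box plots and listings. Means can hide individual outliers.
- Appendix 1 has an adverse-event rule for subjects already abnormal at screening: worsening to CTC AE grade 2, confirmed by three repeated measurements, with investigator discretion to record it sooner. After a first abnormal value at Week 4, 12, 24, 36 or 48 there are 4, 3, 2, 1 or 0 later scheduled safety laboratory visits (Protocol 6.5.4). If three later scheduled visits are needed, no change is confirmed by Week 24. If the first value counts as one of the three, only a change first seen at Week 4 is.

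**The case against.** A reader might infer that worsening in these patients goes uncounted altogether. The documents do not support that. The sentence that plans the notable-value summary also plans unrestricted shift tables, all laboratory data are listed, the protocol plans change from baseline by visit, and Appendix 1 has its own adverse-event rule for subjects already abnormal. What is missing is the notable-value incidence itself; none of these outputs supplies it.

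The exclusion is also one reading rather than a certainty. *New* in SAP 4.6.2.2 could mean not notable at baseline, which would count the patient going from 2.0 to above 3 x ULN. Indeed, if only patients normal at baseline could qualify, the word would add little. The laboratory manual might also cover patients abnormal at baseline. Both arguments have force, but *new* is undefined, the section defers to a protocol table whose title states a restriction, and the SAP names two sources. Two programmers could produce different tables from the same data.

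It is fair, too, that SAP 4.6.2.2 speaks of numbers of patients and that the denominator is only a default. The default nevertheless governs any percentage shown, and Protocol 9.5.3 plans an incidence. Finally, the table is descriptive, has no hypothesis test and treats both arms alike.

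**Conclusion.** The point holds as a mismatch between numerator and denominator in one descriptive safety table. Followed literally, the plan understates the notable-value incidence in both arms. It does not touch the primary or key secondary analysis.

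Two stronger inferences should not be drawn. First, the size is unknown: the figures above only show how the result depends on f, rN and rA, all assumed, and they presume that every patient abnormal at baseline is excluded. Second, the claim that the excluded patients are those closest to the limits is shown for AST and ALT only. It is not shown for WBC or neutrophils, and it does not apply to limits set relative to baseline.

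The change is still worth making: the restriction is stated in the table title, no other planned output replaces the incidence, and the remedy uses data already collected.

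**What to change.** For the analysis only, in SAP 4.6.2.2:
- Apply the numeric limits of Table 12-1 to every patient with a baseline and a post-baseline value for the test.
- Define *new* as meeting the limit after baseline and not at baseline.
- Use the patients at risk for each test as the denominator.
- Show the rows by baseline status, normal or abnormal.
- Leave patients who already meet a limit at baseline (for example platelets below LLN) to the shift tables, since they can never be new under this definition.
- Reconcile SAP 2.3.2.2 and 4.6.2.2 on whether the protocol or the laboratory manual is the source of the limits.

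The adverse-event documentation rule in Appendix 1 is not changed. The cost is SAP wording and a modest change to one table layout, with no new data. The downside is that reported incidences become somewhat higher.

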### **6.5.4 Laboratory evaluations**

Blood samples for safety laboratory evaluation will be taken at screening, baseline, Week 4, Week 12, Week 24, Week 36 and Week 48 (Visits 1, 2, 4, 8, 14, 15, and 16). A central laboratory will be used for analysis of all specimens collected. Details on the collections, shipment of samples and reporting of results by the central laboratory are provided to investigators in the laboratory manual. Following laboratory parameters will be performed locally: urine pregnancy tests, urinalysis strip test and ESR. For more details refer to [Table 6-1](#).

Clinically notable laboratory findings are defined in [Appendix 1](#).

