2.3.2.2 Laboratory parameters

For the identification of notable values, the laboratory manual should be consulted. The following laboratory categories will be listed.

Hematology

Blood will have been obtained at screening, baseline, week 4, week 12, week 24, week 36 and week 48 (or as required at an unscheduled visit) to measure erythrocytes, hematocrit, hemoglobin, leukocytes, platelets, basophils (absolute and percentage), eosinophils (absolute and percentage), lymphocytes (absolute and percentage), monocytes (absolute and percentage), neutrophils (absolute and percentage).

Clinical Chemistry

Blood will be obtained at screening, baseline, week 4, week 12, week 24, week 36 and week 48 (or as required at an unscheduled visit) to measure alanine aminotransferase, albumin, alkaline phosphatase, aspartate aminotransferase, total bilirubin, calcium, serum creatinine, gamma glutamyl transferase, potassium, total protein, sodium, uric acid, total cholesterol, HDL cholesterol, LDL cholesterol, rheumatoid factor, cyclic citrullinated peptide antibody, immunoglobulin A, immunoglobulin G,

Coagulation

Activated Partial Thromboplastin Time (aPTT) and INR.

Urinalysis

Dipsticks will be provided by the central laboratory to the sites for local urinalysis assessments. The sites will record the results in the appropriate eCRF page for each patient.

Measurements for density, pH, glucose, cells (RBC, WBC), proteins, blood and cylinders will be done at screening, baseline, week 4, week 12, week 24, week 36 and week 48 (or as required at an unscheduled visit).

Vital signs

Vital signs include blood pressure and heart rate measurements and will be assessed at all visits. The repeat sitting measurements will be made at 1-2 minute intervals and the mean of the three measurements will be used and entered on the corresponding eCRF page.

ECG

Standard 12-lead ECG measurements will be assessed at time points as per the study schedule (screening, week 24 and week 48). ECG results are captured in the eCRF as “Normal” “Abnormal, clinically insignificant” and “Abnormal, clinically significant”. Any abnormal clinically significant ECG findings should be recorded as adverse events.

Physical examination

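### Table 12-1 flags lymphocytes only when high, so under it a lymphocyte fall enters the notable-abnormality counts only if total white cells drop below 0.8 x LLN; the SAP also names two sources for notable values

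*Protocol*

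**What the plan says.** Protocol section 6.5.4 states that "Clinically notable laboratory findings are defined in" Appendix 1. Table 12-1 there is headed "Notable laboratory values for subjects with value within limits of normal at baseline". Its lymphocyte row reads "Absolute Lymphocyte count > 1.1 x ULN", and the same limit stands in both unit columns. The neighbouring rows look downward: "White Blood Cell count < 0.8 x LLN" and "Absolute Neutrophil count < 0.9 x LLN".

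Notable status has consequences during the study and at its end:

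- **Forwarding (Appendix 1):** "Clinically notable values will be forwarded to the Sponsor at the same time that they are sent to investigators by Central Laboratory".
- **AE documentation (Appendix 1):** a notable value becomes an adverse event after confirmation by three repeat measurements at later visits.
- **Reporting:** protocol section 9.5.3 plans an incidence summary of notable values. SAP 4.6.2.2 plans a count by treatment group and study period, and a separate listing.

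On the source of the thresholds, SAP 2.3.2.2 says: "For the identification of notable values, the laboratory manual should be consulted". SAP 4.6.2.2 instead has "The summaries presenting a number of patients with new notable abnormalities (according to the protocol"). SAP section 3, on changes to planned analyses, mentions no change in the definition.

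**The concern.** Both arms receive adalimumab on background methotrexate. Protocol section 5.5.8 names these two as the exceptions to its ban on DMARDs and immunosuppressants. Comparing the products on clinical laboratory parameters is a stated secondary objective. The table meant to pick out laboratory values for attention nevertheless has no low-side rule for lymphocytes, and neither document explains the direction.

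The SAP's list of events of special interest (Appendix 3) does not fill the gap. It names leukopenia, neutropenia and decreased white blood cell count, but no lymphopenia term.

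If the two products differed in lymphocyte falls, the by-arm table and listing of new notable abnormalities could miss the difference. The two named sources add a second uncertainty: if the laboratory manual and Table 12-1 differ, the count depends on which one the programmer opens.

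**Working it through.** The plan gives no figure to reproduce, so the check compares the rows and then asks whether another row could stand in.

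**1. Direction of each blood-cell row in Table 12-1**

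| Row | Criterion | Flags |
|---|---|---|
| Hemoglobin | decrease of more than 20 g/L from baseline | fall |
| Red cells | more than 20% below baseline | fall |
| Platelets | < LLN | fall |
| White cells | < 0.8 x LLN | fall |
| Neutrophils | < 0.9 x LLN | fall |
| Lymphocytes | > 1.1 x ULN | rise only |

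Five of six rows flag falls. No lymphocyte fall can be counted through the lymphocyte row.

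**2. Can the white-cell row stand in?** Write W = L + O, where W is total white cells, L lymphocytes and O all other white cells. The row fires only if L + O < 0.8 x LLN(W). If O is at or above 0.8 x LLN(W), it does not fire even at L = 0. This step needs no assumed limits.

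**3. Illustration.** The documents give no reference limits. Assumed, in 10^9/L: white-cell LLN 4.0, neutrophil LLN 1.8, lymphocyte ULN 4.0 and LLN 1.0. The flagging limits are then:

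- white cells: 0.8 x 4.0 = 3.2
- neutrophils: 0.9 x 1.8 = 1.62
- lymphocytes: 1.1 x 4.0 = 4.4 (high side)

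*Patient A:* white cells 6.0, neutrophils 5.3, lymphocytes 0.4. Lymphocytes are 60% below the assumed LLN ((1.0 - 0.4)/1.0). None of the three criteria is met, since 6.0 > 3.2, 5.3 > 1.62 and 0.4 < 4.4.

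*Patient B:* O = 4.2 and lymphocytes fall from 1.8 to 0.2. Total white cells go from 6.0 to 4.4, which is above 3.2.

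*Range:* for an assumed white-cell LLN of 3.5 to 4.5, the limit runs from 0.8 x 3.5 = 2.8 to 0.8 x 4.5 = 3.6. Neither patient's total white-cell count reaches it.

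**4. Sources of the rule, side by side**

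| Place | Source named |
|---|---|
| Protocol 6.5.4 | Appendix 1 |
| SAP 4.6.2.2 (specifies the counts) | the protocol |
| SAP 2.3.2.2 (describes the assessments) | the laboratory manual |

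Nothing says that the sources agree or which prevails.

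**The case against.** Four points can be made on the other side.

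**Lymphocyte falls are not lost.** This stands. Protocol 7.1 tells investigators to look for clinically significant results among values outside normal ranges and among marked changes from baseline, so AE reporting is not tied to Table 12-1. Appendix 1 adds investigator discretion, and a grade 2 rule for values already abnormal at screening. Protocol 9.5.3 plans by-visit summaries. SAP 4.6.2.2 plans hematology shift tables by toxicity grade, box plots and listings of all laboratory data. These routes have limits: the AE routes rest on judgement or on an abnormal screening value, the toxicity scale is not named in SAP 4.6.2.2, and the box plots cover unnamed parameters.

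**The count has a stated rule.** This also stands. A reader might infer that the by-arm counts have no defined basis, but SAP 4.6.2.2 does name the protocol. The conflict comes from one sentence in SAP 2.3.2.2, and no document shows that the manual's limits differ.

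**The Appendix 1 AE route is slow.** Safety laboratory visits after baseline are at weeks 4, 12, 24, 36 and 48. If three later visits must confirm a week 4 value, confirmation comes at week 36. A low-side row would therefore not have been a prompt AE trigger, although forwarding to the sponsor does not wait for confirmation.

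**The high-side direction may be deliberate.** Leukocytosis is on the special-interest list, so an interest in high counts is not out of place. The documents do not show the row to be a mistake, and intent has to be asked.

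**Conclusion.** The point holds for Table 12-1 as written. Lymphocyte falls enter the by-arm count and listing of new notable abnormalities, and the forwarding of notable values to the sponsor, only when total white cells also drop below 0.8 x LLN. The two sources named for notable values need reconciling.

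A reader might go further and infer that a lymphocyte fall can never be a notable abnormality in this trial, or that a product difference in lymphocytes would go unseen. The documents support neither. The laboratory manual is not among them and may hold a low limit, and the shift tables, by-visit summaries, full listings and AE routes remain.

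The size is modest: a gap in descriptive safety reporting, with no effect on the primary or key secondary analyses. How many patients would be affected cannot be said, because the documents give no frequency of lymphopenia. The numerical patients rest on assumed reference limits; the row comparison and the white-cell inequality do not.

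**What to change.** 1. Have the sponsor confirm whether the high-only direction of the lymphocyte row is intended.
2. Add a low-side lymphocyte criterion to the SAP's derivation of notable abnormalities, at a level set by the sponsor's medical lead. Keep the existing upper limit, and record the addition in SAP section 3.
3. Re-flag the differentials already collected. Absolute lymphocytes are in the hematology panel at every safety laboratory visit, so no new data are needed.
4. Reconcile SAP 2.3.2.2 with SAP 4.6.2.2 and protocol 6.5.4 so that one named source governs the counts. Appendix 1 with the added criterion is the natural choice, since two of the three places already lead there.

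The cost is one derivation rule, one SAP sentence and a few more flagged values. Changing Table 12-1 itself would need a formal amendment under protocol 11.1. All patients were already randomized at Amendment 3, and the SAP cites blind data review minutes of 19 March 2018. For this trial the gain is therefore mainly in the by-arm table and listing, not in alerting during the study.
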